Ascending fixed-dose cohorts of CC-122 starting at 0.5 mg up to a maximum of 4.0 mg or NTD, whichever occurs first, in combination with ibrutinib will be evaluated. After completion of the 0.5 and 1.0 mg fixed-dose cohorts, subsequent cohorts will be allowed to escalate in either 0.5 mg or 1.0 mg increments. Escalation to the next dose level requires 0/3 or $\leq 1/6$ DLTs at the current dose level. Further, an escalation increment of 1.0 mg requires the absence of any Grade 3 drug related non-hematologic AEs, any Grade 4 hematological event, and TLS or TFR of any grade at the current dose level. The SRC will make the recommendation of whether to open the next dose cohort and the incremental increase in dose (0.5 or 1.0 mg) after review of the safety data of the current dose cohort (after full enrollment and completion of the DLT evaluation period).

CC-122 will be initiated on Cycle 2 Day 1 and administered on a 5/7-day schedule. Ibrutinib will be administered QD starting on Cycle 1 Day 1 (see Section 8.2 for Treatment Description, Administration and Schedule).

CC-122 and ibrutinib will be administered up to a maximum of 24 cycles of CC-122, or until disease progression, unacceptable toxicity, or discontinuation for any other reason, whichever is earlier. In the event CC-122 is discontinued prior to ibrutinib or if patients have surpassed the 24 cycles of CC-122, Celgene will continue to provide an additional 3 cycles of ibrutinib from the investigational supply to allow time for patients to be switched to commercially available ibrutinib and/or other therapies at the discretion of the treating physician. Subjects will be observed for early DLTs for 28 days following the initiation of CC-122 combination therapy (Cycle 2 Days 1 through 28) (DLT evaluation period). Monitoring for late toxicities necessitating dose reductions or discontinuations will be conducted during the first 6 cycles of combination treatment.

Arm C (CC-122 + obinutuzumab):

The following arm will be evaluated in parallel to Arms A and B:

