Ascending fixed-doses cohorts of CC-122 starting at 0.5 mg up to a maximum of 4.0 mg or NTD, whichever occurs first, in combination with obinutuzumab will be evaluated. After completion of the 0.5 and 1.0 mg fixed-dose cohorts, subsequent cohorts will be allowed to escalate in either 0.5 mg or 1.0 mg increments. Escalation to the next dose level requires 0/3 or $\leq 1/6$ DLTs at the current dose level. Further, an escalation increment of 1.0 mg requires the absence of any Grade 3 drug related non-hematologic AEs, any Grade 4 hematological event, and TLS or TFR of any grade at the current dose level. The SRC will make the recommendation of whether to open the next dose cohort and the incremental increase (0.5 or 1.0 mg) after review of the safety data of the current dose cohort (after full enrollment and completion of the DLT evaluation period).

CC-122 will be initiated on Cycle 1 Day 9 and administered on a 5/7-day schedule. For subjects on Arm C, Cycle 1 only will consist of 29 days to accommodate the 5/7-day schedule; subsequent cycles will consist of 28 days. Obinutuzumab will be administered intravenously on Cycle 1 Days 1, 2, 8, and 15 (see Section 8.2 for Treatment Description, Administration and Schedule). The dose of obinutuzumab on Day 1 and Day 2 of Cycle 1 may be adjusted per institutional practice provided the combined dose equals 1000 mg. Obinutuzumab will be administered on Day 1 every cycle thereafter up to Cycle 6.

CC-122 will be administered up to a maximum of 24 cycles of CC-122, or until disease progression, unacceptable toxicity, or discontinuation for any other reason, whichever is earlier. In the event CC-122 is discontinued prior to obinutuzumab, Celgene will continue to supply the protocol-specified total of 6 cycles of obinutuzumab. In addition, for patients that have surpassed the 24 cycles of CC-122, Celgene will continue to provide an additional 3 cycles of CC-122 to allow time for patients to be switched to commercially available therapies at the discretion of the treating physician.

Subjects will be observed for early DLTs for 28 days following initiation of CC-122 combination therapy (Cycle 1 Day 9 through Cycle 2 Day 8) (DLT evaluation period). Monitoring for late toxicities necessitating dose reductions or discontinuations will be conducted during Cycles 2 through 6.

Early DLT Evaluation of Intrasubject Dose Escalation Cohort in Arm A:

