8.2.10. Management of Select AEs While Receiving Obinutuzumab

8.2.10.1. Infusion-Related Reactions (IRRs)

Two-thirds of patients experienced IRRs with the first infusion of obinutuzumab; reactions can also occur with subsequent infusions, but the frequency is lower ([GAZYVA](#), [GAZYVARO](#)). Infusion reactions typically occur within 24 hours of receiving obinutuzumab. Symptoms may include anaphylaxis, acute life-threatening respiratory symptoms, hypotension, tachycardia, dyspnea, bronchospasms, larynx and throat irritation, wheezing, and laryngeal edema. Additional potential symptoms include nausea, vomiting, diarrhea, hypertension, flushing, skin rash, urticaria, headache, pyrexia, and chills.

To minimize the potential for these reactions, premedication is administered as described in Section 9.3.3. Full emergency resuscitation facilities should be immediately available in the event of a severe and life-threatening infusion reaction and subjects should be under close supervision of the investigator or appropriately trained staff during the infusions. Medical

management of infusion reactions should be instituted according to standard medical practice using glucocorticoids, epinephrine, oxygen, intravenous fluids and other medications as medically indicated. Subsequent infusions should be administered with appropriate premedications as in Section 9.3.3.

Subjects with pre-existing cardiac or pulmonary conditions should be monitored more frequently throughout the infusion and after the infusion. Hypotension may occur and investigators should consider withholding antihypertensive agents (for subjects not at risk for hypertensive crisis) for 12 hours prior to, during the infusion, and for 1 hour after the infusion until blood pressure is stable.

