Ascending fixed-dose cohorts of CC-122 starting at 0.5 mg up to a maximum of 4.0 mg or NTD, whichever occurs first, in combination with ibrutinib will be evaluated. After completion of the 0.5 mg and 1.0 mg fixed-doses cohorts, subsequent cohorts will be allowed to escalate in either 0.5 mg or 1.0 mg increments. Escalation to the next dose level requires 0/3 or $\leq 1/6$ DLTs at the current dose level. Further, an escalation increment of 1.0 mg requires that absence of any Grade 3 drug related non-hematologic AEs, any Grade 4 hematological event, and TLS or TFR of any grade at the current dose level. The SRC will make the recommendation of whether to open the next dose cohort and the incremental increase in dose (0.5 or 1.0 mg) after review of the safety data of the current dose cohort (after full enrolment and completion of the DLT evaluation period).

CC-122 will be initiated on Cycle 2, Day 1 and administrated on a 5/7-day schedule. Ibrutinib 420 mg daily dose (QD) will be administered starting on Cycle 1, Day 1 (see Protocol Section 8.2 for treatment description, administration and schedule).

CC-122 and ibrutinib will be administered up to a maximum of 24 cycles of CC-122, or until PD, unacceptable toxicity, or discontinuation for any other reason, whichever is earlier. In the event CC-122 is discontinued prior to ibrutinib or if patients have surpassed the 24 cycles of CC-122, Celgene will continue to provide an additional 3 cycles of ibrutinib from the investigational supply to allow time for patients to be switched to commercially available ibrutinib and/or other therapies at the discretion of the treating physician.

Subjects will be observed for early DLTs for 28 days following the initiation of CC-122 combination therapy (Cycle 2, Days 1 through 28) (DLT evaluation period). Monitoring for late toxicities necessitating dose reductions or discontinuations will be conducted during the first 6 cycles of combination treatment (see Section 17.2.2 for CC-122 Cycle definition).

Arm C (CC-122 + obinutuzumab):

The following arm will be evaluated in parallel to Arms A and B:

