 - First dose date of IP corresponds to the earliest date any dose (of CC-122, ibrutinib, or obinutuzumab) has been initiated (i.e. a non-zero dose was administered/infused).
 - Last dose date of IP corresponds to the latest date any dose (of CC-122, ibrutinib, or obinutuzumab) has been administered/infused.
- 

Time points beyond Cycle 12 will not be displayed in the by cycle summary due to limited sample size and the allowed flexible frequency of the test/measurement. Data from all time points will be included to evaluate the “most extreme” post-baseline value.

- For subjects in Arm A who have disease progress (PD) and then are treated with Ibrutinib or Obinutuzumab, following conversions will be applied:

- In the database, the cycles after PD/arm switch will be labeled with suffix “-PD” and started from “Cycle 1 Day 1”. For summary and reporting purpose, those visits will be mapped to the cycle numbers based on their original treatment schedule. For example, if a subject switch to Arm B (CC-122 plus Ibrutinib) after Cycle 2, the next visit labeled as “Cycle 1 Day 1 - PD” will be mapped as “Cycle 3 Day 1” and summarized accordingly.
 - Efficacy data collected up to the PD/arm switch, and all safety data collected in the study will be included in the summary under Arm A (and the starting dose level of CC-122 they initially received).
 - For study treatment and exposure summaries, the data collected before the treatment switch will be summarized under “CC-122 xx mg” according to the subject’s initial CC-122 dose, the data collected after the treatment switch will be summarized under “CC-122 + Ibrutinib”, or “CC-122 + Obinutuzumab”, according to which drug the subject received.
 - Subjects who switch the treatment can report AEs which are
 - related to Ibrutinib or Obinutuzumab,
 - leading to discontinuation/reduction/interruption of Ibrutinib or Obinutuzumab.

Those TEAEs will be summarized under Arm A (and starting dose of CC-122 they initially received).

- For subjects in Arm C who are not treated with CC-122:

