In the analysis based on Safety population, “Obinutuzumab Only” group will be used to summarize these subjects in Arm C who discontinue treatment/study without treatment of CC-122. In addition, “Arm C Total CC-122” and “Arm C Overall” group will be used to summarize the subtotal results without and with these subjects, respectively. In listings which are related with study drug and safety evaluations, “Arm/CC-122 dose” column will be displayed as “Arm C/0.0 mg” for these subjects.

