11.1. Adverse Events

11.1.1. Summary of Adverse Events

AEs will be analyzed in terms of Treatment-Emergent Adverse Events (TEAEs) which are defined as any AEs that begin or worsen on or after the start of IP through 28 days after the last dose of IP. All AEs will be coded using the MedDRA® dictionary Version 22.0 or higher.

If a subject experiences the same AE more than once with a different toxicity grade, then the event with the highest grade will be tabulated in “by grade” tables. If a subject experiences multiple AEs under the same PT (SOC), then the subject will be counted only once for that PT (SOC). In addition, AEs with a missing intensity will be presented in the summary table as an intensity category of “Missing” and will not be imputed.

The incidence of TEAEs will be summarized by MedDRA SOC and PT. The intensity of AEs will be graded 1 to grade 5 by investigator according to the National Cancer Institute Common Terminology Criteria for Adverse Events (NCI CTCAE) Version 4.03 with the exception of tumor flare (NCI CTCAE version 3.0), tumor lysis [REDACTED] and laboratory abnormalities as recommended by the IWCLL guidelines for the diagnosis and treatment of chronic lymphocytic leukemia [REDACTED] For all other AEs, the intensity will be determined by the investigator as mild (Grade 1), moderate (Grade 2), severe (Grade 3), life-threatening (Grade 4) or death (Grade 5).

Tables summarizing the incidence of TEAEs by dose cohort will be generated for each treatment arm with the following:

- TEAEs;
- TEAEs related to CC-122, other combination drug (ibrutinib or obinutuzumab) and CC-122 and/or other combination drug;
- TEAEs of NCI CTCAE grade 3 or 4 by maximum NCI CTCAE grade;
- TEAEs related to CC-122, other combination drug (ibrutinib or obinutuzumab) and CC-122 and/or other combination drug with NCI CTCAE grade 3 or 4 by maximum NCI CTCAE grade;
- TEAEs with death outcome;

- TEAEs with death outcome related to CC-122, other combination drug (ibrutinib and obinutuzumab) and CC-122 and/or other combination drug;
- Serious TEAEs;
- Serious TEAEs related to CC-122, other combination drug (ibrutinib and obinutuzumab) and CC-122 and/or other combination drug;
- TEAEs leading to discontinuation of CC-122, of other combination drug (ibrutinib and obinutuzumab), of CC-122 or other combination drug, of CC-122 and other combination drug;

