17.3. Baseline, Repeated Measurements, and End of Trial

The general conventions for handling baseline, repeated measurements, and End of Trial (EOT) are provided below:

- Baseline for any clinical laboratory test, efficacy endpoints and vital sign is defined as the last value of a specific endpoint measured before the first dose of the IP.

- Baseline values for biomarkers will be the average of non-missing values collected at screening and the last value before first dose of the IP, if both samples are collected. Otherwise, either the values collected at screening or the last value of a specific endpoint measured before the first dose of the IP, whichever is collected, will be used as the baseline. Other pre-dose samples from on-treatment visits after the first dose of the IP will not be used to impute baseline value.
- Central laboratory values will be used; local laboratories will be used only if there is not any central laboratory by first dose date. When there are multiple values for any laboratory test (clinical and biomarker) or vital sign collected at the same visit, the one with last/latest assessment time stamp will be used for data analysis.
- End of trial assessment for a particular endpoint is defined as the last non-missing post-baseline assessment during the study period.
- Adequate efficacy assessment encompasses protocol defined assessments of tumor lesions (lymph nodes, spleen, and liver), peripheral blood test, bone marrow assessment when indicated, and clinical assessment.

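### In Arms B and C the TEAE window and the laboratory and vital-sign baselines start before CC-122, so partner-drug lead-in events enter CC-122 dose-cohort tables with no full period split

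*SAP*

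**What the plan says.** Adverse event incidence and severity is a primary endpoint (Protocol 3.1), and two of the three primary objectives concern the safety and tolerability of a combination (Protocol 2.1).

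**Dosing.** In Arm B, "Ibrutinib 420 mg daily dose (QD) will be administered starting on Cycle 1, Day 1" (SAP 4.1), while "CC-122 will be initiated on Cycle 2 Day 1 and administered on a 5/7-day schedule" (Protocol 4.1). In Arm C, obinutuzumab is infused on Days 1, 2 and 8, and "CC-122 will be initiated on Cycle 1 Day 9 and administered on a 5/7-day schedule" (Protocol 4.1).

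**Clock.** SAP 5.1 treats all three drugs as IP and states: "First dose date of IP corresponds to the earliest date any dose (of CC-122, ibrutinib, or obinutuzumab) has been initiated". SAP 11.1.1 then defines TEAEs as "any AEs that begin or worsen on or after the start of IP through 28 days after the last dose of IP". SAP 17.3 sets the baseline for laboratory tests, efficacy endpoints and vital signs as "the last value of a specific endpoint measured before the first dose of the IP". For both arms that is a value taken before the partner drug.

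**Display.** Safety tables are by arm and dose cohort (SAP 11), and subjects are filed under their starting CC-122 dose (SAP 5.2.1). For Arm C only, SAP 5.1 creates an Obinutuzumab Only group that "will be used to summarize these subjects in Arm C who discontinue treatment/study without treatment of CC-122". Arm B has no such group.

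**The concern.** An event during the lead-in cannot have been caused by CC-122, yet it appears in the all-causality tables under a CC-122 dose. A reader who uses those tables to describe the combination, or to look across dose levels, sees a mixture of two exposure periods. Laboratory and vital-sign changes measured from the pre-partner baseline likewise include changes that were complete before CC-122 began.

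Arm C is the clearer case, because Protocol 8.2.10.1 reports that "Two-thirds of patients experienced IRRs with the first infusion of obinutuzumab" and that infusion falls on Day 1. There is also a gap in the rules. An Arm B subject who stops during the ibrutinib lead-in is in the Safety population but has no starting CC-122 dose to be filed under.

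**Working it through.** The plan states no figure for this point, so there is none to reproduce. The check covers dates, table coverage and scale.

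**Lead-in lengths**
- Arm B: Cycle 1 is 28 days. As a cross-check, Protocol 6.2.2 places the CT after six CC-122 cycles at Week 25 for Arms A and C and at Week 29 for Arm B. Six cycles are 6 × 28 = 168 days, and 168/7 + 1 = 25. With the lead-in, (28 + 168)/7 + 1 = 29. The two agree.
- Arm C: CC-122 starts on Day 9, so the lead-in is 9 − 1 = 8 days. Cycle 1 lasts 29 days, so it holds 8 lead-in days and 29 − 8 = 21 CC-122 days. The lead-in share of Cycle 1 is 8/29 = 28%.

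**What the SAP 11.1.1 tables separate**
- Relatedness tables (CC-122, partner drug, either): they separate by investigator attribution in both arms, including for Grade 3/4 and serious events. They do not separate all-causality counts.
- TEAEs by cycle of onset: these isolate the lead-in in Arm B, where Cycle 1 is ibrutinib alone if CC-122 starts on schedule. They do not in Arm C, where Cycle 1 holds both periods. This reads the plain word cycle as the study treatment cycle of SAP 17.2.2, since other rows say CC-122 cycle expressly.
- Tables by CC-122 cycle of onset: limited to events leading to dose reduction or discontinuation.
- Selected events of interest, plus febrile neutropenia, tumor flare and tumor lysis: may be shown by cycle of onset, but these are chosen terms only.
- All Grade 3/4 TEAEs and all serious TEAEs: no onset-period table is specified in either arm.
- DLTs (SAP 11.1.2): counted from first CC-122 in every arm.

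**Share of time spent in the lead-in**

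For c cycles of CC-122 the share is L/(L + 28c), with L = 28 in Arm B and L = 8 in Arm C. Adding the 28-day follow-up gives L/(L + 28c + 28).

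| CC-122 cycles | Arm B | Arm C | Arm B with follow-up | Arm C with follow-up |
|---|---|---|---|---|
| 1 | 28/56 = 50% | 8/36 = 22% | 28/84 = 33% | 8/64 = 12.5% |
| 6 | 28/196 = 14% | 8/176 = 4.5% | 28/224 = 12.5% | 8/204 = 3.9% |
| 24 | 28/700 = 4.0% | 8/680 = 1.2% | 28/728 = 3.8% | 8/708 = 1.1% |

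These are shares of time. They equal shares of events only if the event rate is constant. Because a subject counts once per preferred term, incidence changes less when the same term recurs under CC-122.

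**Infusion reactions in Arm C**

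Assume the two-thirds rate applies to this trial. The expected number is 2/3 × 3 = 2 in a cohort of three and 2/3 × 6 = 4 in a cohort of six. P(at least one) = 1 − (1/3)^n, which is 0.963 for n = 3 and 0.999 for n = 6. At half that rate, one-third, the expected numbers are 1 and 2, and 1 − (2/3)^n gives 0.704 and 0.912. Either way, most Arm C cohorts would show a TEAE that preceded CC-122.

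**The case against.** Counting from the first dose of any study drug is conventional. It follows Protocol 10.7, which includes everyone who received any assigned IP, and the lead-in is part of the assigned regimen. Attribution tables cover most categories, and an event before any CC-122 should not be recorded as related to it. Arm B's onset tables already isolate its lead-in. AE listings would allow a split afterwards. Cohorts are of three to six subjects, the lead-in is the same in every cohort of an arm, and no dose-response test is planned. All of this stands, and it is why the point is an improvement rather than a correction.

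The objection does not supply an Arm C all-causality table free of lead-in events, a period split of all Grade 3/4 or serious events, or a rule for an ibrutinib-only subject. The documents do not show that such a subject exists, but the rule costs one sentence.

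There is also a fair objection to re-baselining. SAP 17.8 grades platelet and hemoglobin toxicity by the fall from the pre-treatment value, so a later baseline would depart from that scale and could hide an acute fall after obinutuzumab. Some tests, such as lipase, TSH and urinalysis, are not scheduled on Arm C Days 8 or 9 (Protocol Table 5).

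A reader might infer more than the documents support:
- That the MTD is contaminated. It is not, because the DLT window starts at CC-122.
- That the ECG baseline is affected in the same way. SAP 17.3 does not name ECG.
- That obinutuzumab reactions or acute thrombocytopenia will dominate the Arm C tables. Protocol 8.2.10.3 gives no rate for the latter in the available text.
- That a dose gradient is demonstrably diluted. The mechanism is plausible, but nothing in the documents quantifies it.

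**Conclusion.** The point holds as a cheap improvement of minor to moderate weight. The all-causality, Grade 3/4 and serious TEAE tables for Arms B and C pool 28 and 8 days of partner drug alone with the combination period, under a CC-122 dose label. What remains unseparated is the Arm C lead-in in all-causality tables, the onset period of all Grade 3/4 and serious events in both arms, and the placement of an Arm B subject who never takes CC-122. The effect is largest for subjects with short exposure and small for those who reach 24 cycles. The infusion-reaction counts rest on a general obinutuzumab rate carried over to this trial. The time shares assume dosing on schedule.

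**What to change.** Keep the any-IP tables as they are, and make three additions.

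1. For Arms B and C, add TEAE tables (all, Grade 3 or higher, serious) restricted to events that start or worsen on or after first CC-122, in subjects who took CC-122. Show lead-in events separately as ibrutinib alone and obinutuzumab alone. SAP 17.2.2 already defines the CC-122 start needed.
2. Add an Ibrutinib Only group for Arm B that mirrors the Arm C rule in SAP 5.1, with matching subtotals.
3. As a supplement, show change and CTCAE shift from the last value before first CC-122, only for tests scheduled then. CBC and chemistry qualify at Arm B Cycle 2 Day 1 (Protocol Table 4) and Arm C Days 8 and 9 (Protocol Table 5), with samples predose by default (Protocol 6.1.8). Leave IWCLL platelet and hemoglobin grading on the pre-treatment value.

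The cost is SAP wording and further table runs on data already scheduled for collection. The downsides are more tables, and a second baseline that must be clearly labelled because it would not show falls that occurred during the lead-in.

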11.1.2. Dose-limiting Toxicities (DLTs)

DLT is defined as a treatment-related AE(s) occurring in Cycle 1 (the first 28 days of treatment with CC-122 and combination therapy) that meets one of the criteria defined in the Protocol Section 8.2.7. Subjects will be observed for early DLTs for 28 days following the initiation of CC-122 (for Arm A, Cycle 1 day 1 through Cycle 1 Day 28; for Arm C, Cycle 1 day 9 through Cycle 2 day 8, and for Arm B, Cycle 2 Day 1 through Cycle 2 Day 28) (DLT evaluation period).

A summary table of DLTs during DLT evaluation period will be presented by dose cohort and treatment arm including number and percentage of subjects having a DLT. The percentage of subjects having a DLT is based on the number of subjects who are CC-122 evaluable for DLT Evaluable population. Listing of AEs which meet dose limiting toxicity will be provided.

